12.2. Training of Staff

As per GCP, each individual involved in the conduct of a study will be qualified by education, training and experience to perform his or her respective task(s). The PI will maintain a record of all individuals involved in the study. The PI will ensure that appropriate training relevant to the study is given to staff, and that they will receive any new information of relevance to the performance of this study.

12.3. Changes to the Protocol

Study procedures will not be changed without the mutual agreement of the PI and the Sponsor. If it is necessary for the study protocol to be amended, the amendment or a new version of the study protocol must be approved by the HREC before implementation unless the safety of participants is at risk. Local requirements must be followed. If a protocol amendment requires a change to the PICF, approval of the revised PICF by Orygen and by the HREC is required before the revised form can be used to consent potential participants.

12.4. Protocol Compliance

The study shall be conducted as described in the approved protocol. All revisions to the protocol must be discussed with Orygen. The investigator should not implement any deviation or change to the protocol without prior review and documented approval from the HREC of an amendment, except where necessary to eliminate an immediate hazard(s) to study participants. Any significant deviation must be documented in the source documentation. If a deviation or change to a protocol is implemented to eliminate an immediate hazard(s) prior to obtaining HREC approval

as soon as possible, the deviation or change will be submitted to the HREC for review and approval.

12.5. Study Termination

The planned start date for this study is the date of first patient first visit which we anticipate will be November 2021. The recruitment period will be for 2 years (November 2021- October 2022). The proposed completion date is the date of last patient last visit which we anticipate will be November 2025. The Sponsor, Orygen, reserves the right to terminate the study at any stage for any reason including funding considerations.

12.6. Data handling and record retention

Clinical data collected in the PRESCIENT research network will be entered in the secure online Orygen Research Project Management System (RPMS). The RPMS is login-protected and users can only access the section that pertains to their own recruitment site. Neurocognition data will be collected directly via the PennCNB website. MRI data, actigraphy data, speech samples, video recordings and EEG data will be stored in the University of Melbourne Mediaflux system (<http://www.arcitector.com/mediaflux/features/>). Digital biomarker data will be recorded via the mindLAMP app and stored on an Orygen-based server.

All coded data will be transferred from the Orygen servers/University of Melbourne Mediaflux system to a secure server at the NIMH NDA (NDA Staging Environment). A copy of the data will remain at the Sponsor site on the Orygen servers/University of Melbourne Mediaflux system. The NIMH NDA Staging Environment will only be accessible by the Data Processing Analysis and Coordinating Center (DPACC). DPACC will conduct data monitoring and quality assurance checks on the data on this server. In some circumstances, the DPACC may also require access to some coded participant data on Orygen/University of Melbourne servers for QC and monitoring purposes, prior to it being sent to the NDA Staging Environment (e.g., to check raw neurocognitive scores in addition to the calculated scores transferred to the NDA). Following the DPACC review, the coded data will be transferred to the NIMH NDA Collaboration Space, a data repository maintained and sponsored by the National Institutes of Health (NIH). AMP SCZ investigators, AMP SCZ partners, FNIH and NIH staff will have access to the data in the NIMH NDA Collaboration Space for monitoring and data analysis purposes (subject to execution of an NDA Data Access Agreement). Every six months the NIMH NDA will make the curated data available to the general research community (NDA Curated Releases).

The raw audiovisual data will remain on the University of Melbourne Mediaflux system. Only processed audiovisual data (i.e., variables extracted from the raw data) will be transferred to the NIMH NDA. The raw passive sensing data, including

geolocation data, will be transferred to the NIMH NDA and included in the NDA Curated Releases. Investigators who access this raw passive sensing data via the NIMH NDA will require institutional ethics committee approval to do so (see 15.2). The reason for transferring raw geolocation data to the NIMH NDA is that such data holds significant promise for the development of novel environmental risk metrics. Providing this data to the general research community will aid the development of such measures for use in future studies, which may in turn contribute to the identification of risk and resilience factors in this high risk clinical population.

All study documentation will be retained indefinitely (following completion of the study) including participant files and other essential documents (study protocol, signed informed consent forms, correspondence, and other documents pertaining to the conduct of the study). Should the Investigator wish to assign the study documentation to another party or move to another location, Orygen must be notified.

In addition, the Investigator should notify Orygen prior to destruction of any study documentation, regardless of the timeframe lapsed.

The Sponsor should notify the Investigator/Institution in writing if/when study-related records are no longer required to be kept.

13. Data Management

13.1. Documentation

A screening log of all potential participants specific to the recruitment site will be maintained by the site. This will include potential participants who were considered but later deemed ineligible due to meeting one of the exclusion criteria or due to investigator discretion. The reasons for exclusion or refusal will also be recorded against their ineligibility/refusal status. This log will be stored securely and locally by the recruitment site. All participants who are considered for or enrolled in the study will receive an individual identification number. The RA Procedures Manual provides more in-depth information regarding the screening log and enrolment of participants. Documentation regarding potential participants and participants enrolled in the study will only be accessible to site study team members who need this information for conducting the study. Confidentiality will further be maintained by assigning each subject a study-specific number, and coding all data collected with that number, using the NIH Globally Unique Identifier (GUID) tool. All data collection media will use the study-specific identification number to link the data to one individual. Data on the RPMS will only be accessible to study team members from the same site as the participant.

Source data will be constituted as documents where the study data are first recorded. This will include the hard-copy questionnaires and measures, and raw data such as

EEG recordings and neurocognitive computer task responses. These data will be retained in a secure location at or by the recruitment site, accessible only to delegated study team members and relevant site staff.

Electronic Case Report Forms (eCRFs) will also be used for documentation and reporting data to Orygen. For the measures in which the results are entered directly into the eCRF, the eCRF becomes the source documentation.

Research Assistants or other appropriate delegates will be responsible for entering data into the eCRF.

Study monitoring will be performed in accordance with the monitoring plan developed by Sponsor Operations in conjunction with the study team and the DPACC. This will be augmented by the study's quality control plan.

13.2. Database management

Internet-based database applications will be used at Orygen and by international collaborators for the Case Report Form, with relevant data being entered online. The database applications will be modelled on previous studies that have adopted the eCRF data collection method. Data collected in the eCRF will be entered via a secure website. Access to the eCRF will be restricted to study personnel and the level of access will be set to maintain the privacy and confidentiality of participant information. Data is backed up on a regular basis and an audit trail of entered, amended or deleted data, as well as the staff member who made those changes, is retained. After any monitoring and data management queries are resolved and complete, the study database will be locked and the eCRF signed off by the PI for each participant. All data will be exported into the appropriate software to enable statistical analysis on secure Orygen or collaborator servers. All study team members will need to apply for access to the eCRF through the study's Project Manager or coordinating investigator. These processes will be recorded and kept with the study essential documentation.

This study has received funding from the National Institute of Health (NIH) in the USA, and as part of this funding agreement, pseudo-anonymised (coded) data will be submitted to the National Institute of Mental Health NIMH Data Archive (NDA) and the NIMH Repository and Genomics Resource (NRGR) based in the USA (see data flow description in 12.6). The NDA and NRGR are data repositories run by NIMH that allows researchers studying mental illness to collect and share pseudo-anonymised information with each other to progress scientific research.

The act of pseudo-anonymising information will ensure that all personal information about research participants is removed and replaced with a code number. This then becomes re-identifiable (coded) information and means the research team will have the link between the participant's personal identifying information and the coded data should the need to re-identify the participant arises. The principal investigator and

study team will keep the personal identifying information and matching unique code in a securely protected database. The DPACC will only access the coded data and will not access personal identifying information or the link between the coded data and personal identifying information. The only exception to this is that the DPACC will access dates when assessments were completed.

As described, this is an international study and international data transfer is going to occur. Data flow is described appropriately in the consent forms and in relevant data management procedural documentation. All data will be transferred securely, at highest industry standards, and in accordance with applicable privacy and confidentiality requirements.

13.3. Protocol Deviations and Suspected/Serious Breaches

13.3.1 Protocol Deviations

Deviations are any (minor or major) breach, divergence or departure from the requirements of Good Clinical Practice or the clinical trial protocol. A protocol deviation is a less serious non-compliance with the approved study protocol. Examples of protocol deviations may include:

- 1) Missed visits
- 2) Missed assessments
- 3) Visits/assessments performed early or later than scheduled date.

13.3.2 Suspected Breaches

A suspected breach is a possible serious breach of GCP or the protocol which has been identified by a third party (other than the Sponsor, e.g., the investigator) but has yet to be formally confirmed as a serious breach by the Sponsor. An example of suspected breaches include missing consent forms.

13.3.3 Serious Breaches

A serious breach is a breach of GCP or the protocol that is likely to affect to a significant degree:

- a) The safety or rights of a study participant, or
- b) The reliability and robustness of the data generated in the study

Examples of potential serious breaches include:

- Participant Informed Consent:
 - Confirmation that consent is not obtained
- Missed study visits or reduced contact due to error by study team that impacts on participant safety.

14. Statistical Methods

The details of the analytical approach will be determined based on ongoing consultation with the DPACC and the NIMH Steering Committee. A Data Analysis Team is currently being established with representatives from the DPACC, PRESCIENT, ProNET, NIMH, and AMP SCZ partners. However, a broad outline of the likely statistical methods is outlined below. It is expected that a variety of interim analyses may be agreed upon by relevant stakeholders.

Testing current and forthcoming prediction models (aims 2a, 2b)

The scale and range of data collected in the PRESCIENT network will allow external validation of existing and forthcoming prediction models in the field. Specifically, the CHR prediction models and risk calculators for psychosis conversion that have already been published, summarised in a number of reviews^{8, 116, 117}, will be tested for performance in this newly recruited large sample. There are also a number of forthcoming CHR prediction models that can be tested in the current dataset, including those from the EU-GEI¹¹⁸, Pronia⁶⁴, Psyscan¹¹⁹, and IPPACT¹²⁰ studies. The multimodal data to be collected in PRESCIENT will be of sufficient depth and breadth to test all of these models.

Of the existing prediction models in the field, the one that shows the strongest performance in the PRESCIENT sample may be made into an online risk calculator for preliminary use in some clinical settings (e.g., to allow clinical decision-making regarding the value of further assessments, such as referral for imaging), as in other areas of medicine^{e.g.121}, and to allow stratification for aetiological and treatment research. Importantly, because the PRESCIENT dataset will include participants recruited from both primary and specialist service settings (*headspace* and HEPs/Orygen), the risk calculator will be able to be calibrated for type of recruitment/service setting, which has been found to be an important factor in risk prediction in this field¹²². This use of the PRESCIENT dataset to externally validate existing and forthcoming prediction models will address one of the key limitations in the field⁹, namely the lack of robust validation procedures on prediction models.

Developing new prediction models (specific aim 2c)

Critically, the PRESCIENT dataset will facilitate the development of new, more refined prediction models, and associated risk calculators, that take advances in the field into account (such as iterative and dynamic prediction, see 2.3) and which directly address the limitations identified in the field (lack of internal and external validation; low ratio of converted cases to number of predictor variables; lack of pre-selection of predictor variables; inappropriate methods of presenting model performance; not covarying for treatment received; insufficient use of clinical

comparison groups^{9, 123, 124}). Data from the PRESCIENT and ProNET networks will be combined (i.e., the AMP SCZ dataset) for the development of these new prediction models. The primary purpose of these new prediction models will be to guide stratification of patients in future pharmacological clinical trials, in line with the overarching aim of AMP SCZ to develop new treatments for the CHR stage of illness.

There are a number of reasons that the AMP SCZ dataset will be able to *improve* on prediction models based on existing datasets and which may be far more useful for treatment decision-making and treatment development:

1. *Scale and multimodal data*: The size of the dataset (approximate CHR n of 2000) and the comprehensive suite of multimodal data will provide greater predictive accuracy in model development and allow the integration of multiple data types.

2. *Dynamic prediction*: There is compelling preliminary evidence that using repeat assessments over time can enhance predictive performance and provide early warning signs of deterioration or lack of treatment response. This modelling requires time series data, which is not extensively available in existing data sets, but will be collected in this new network. A variety of methods will be used to collect the required data (see 8.1 Schedule of Assessments): repeat biomarker data to examine predictive value of biomarker trajectories; in-person and online clinical, neurocognitive, and speech data; and digital assessment methods, including EMA and passive sensing (actigraphy and geolocation). The research team has developed and has access to world leading applications for both EMA and passive sensing. These dynamic aspects of predictive modelling may provide risk calculations based on trajectories in individual-level data and which can be updated over time in response to incoming information, providing recommendations for change in treatment approach (e.g., increase in risk indicating the need for intensification of treatment). They also have the potential to provide 'real time' indications of imminent deterioration in mental state.

3. *Modelling impact of treatment*: Most CHR patients included in research cohorts receive psychosocial and/or pharmacological treatment, even if 'standard care' rather than controlled trial treatment. There has been increased recognition in recent years that this treatment (both as pre-emptive and for presenting complaints) *influences outcomes*, i.e., prediction models may in fact be modelling treatment response rather than natural course of disorder, or possibly an interaction between the two^{123, 125}. The impact of type/degree of treatment components delivered (e.g., psychosocial interventions, medications, nutritional supplements, etc.) will be captured and incorporated into predictive modelling.

Both traditional statistical and machine learning approaches will be deployed in development of prediction models. Statistical approaches will include Cox regression and joint modelling. While the selection of variables to be measured in the study are already informed by their predictive performance in previous studies, variable selection methods including LASSO and stepwise selection will be used to select

potential predictors in the final model. The candidate predictors include the range of multimodal assessments outlined in 8.1. Due to the high number of predictor variables, data reduction procedures may be used. Internal validation of the model will be conducted using bootstrap validation (a resampling technique). The performance of the prediction models will be assessed using measures such as sensitivity, specificity and concordance index (which should be at least 0.7 for good predictive performance). Machine learning approaches will include support vector machine (SVM) algorithms using model training and leave-one-site-out cross validation.

External validation (specific aim 3)

If a strong prediction model can be obtained, further evaluation of the prediction model will be conducted by using an external validation sub-sample from the AMP SCZ cohort. Data from a subset of sites across the two networks will be held back from the initial model development phase in order to externally validate the performance of the model. This will test the replicability of the model's performance and the generalisability of the findings to diverse healthcare settings. Calibration performance of the model will be assessed using calibration plot (plot of predicted outcome probabilities against observed outcome frequencies) and tests for calibration intercept and slope. Discrimination performance will be assessed using measures such as sensitivity, specificity and concordance index.

15. Publication and Use of Study Findings

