---	---

Primary Objectives
	
1. CHR Network Consolidation: Use the Australian Early Psychosis Collaborative Consortium (AEPCC) national platform to consolidate a network of CHR recruitment centres organised according to a ‘hub and spoke’ model, with Orygen functioning as the central hub with 1 Australian and 9 non-Australian clinics as spokes. The network will: recruit a large sample of CHR patients (n=937) and a healthy control (n=250) sample; implement repeated multimodal assessments; map trajectories and outcomes over a 2 year period (conversion to psychotic disorder, persistent and incident non-psychotic disorders, non-remission of CHR status, persistent negative symptoms, psychosocial functioning, full recovery). This network of CHR recruitment centres will provide the clinical research infrastructure for future treatment trials in this clinical population informed by findings from the current program of work.
 
2. Prediction: In collaboration with the NIMH Steering Committee and the DPACC, the PRESCIENT dataset will be used to:
 
2a. Test the external validity of existing and forthcoming prediction models in the field (e.g., NAPLS, EU-GEI, PRONIA, PSYSCAN).
 
2b. Implement the model with strongest performance as an online risk calculator that can be calibrated for service setting (primary vs specialist settings) and availability of type of data (e.g. clinical data alone, clinical data plus neurophysiological data, polygenic risk score, etc).
 
2c. Use the full AMP SCZ dataset (combined PRESCIENT and ProNET data) to develop new, more refined prediction models and risk calculators using recent theoretical and methodological advances (e.g., dynamic prediction, probabilistic multimodal modelling) and a range of biomarkers. These tools will be of clinical utility in decision making about stepping interventions up/down as risk is assessed over time (clinical trajectory, treatment response) and in response to incoming biomarker information, as well as guide stratification of patients in future clinical trials.
 
3. Validation: Internally and externally validate the prediction models generated using the AMP SCZ dataset. This will test the robustness, replicability and generalisability of the models’ performance.
 
The national and international network of sites and research specialisation will provide the clinical research infrastructure for future treatment trials in this clinical population informed by findings of the current program of work.

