5.4. Study Aims

1. CHR Network Consolidation: Use the Australian Early Psychosis Collaborative Consortium (AEPCC) national platform to consolidate a network of CHR recruitment centres organised according to a 'hub and spoke' model, with Orygen functioning as the central hub with one Australian and nine non-Australian clinics as spokes. The network will: recruit a large sample of CHR patients (n=937) and a healthy control (n=250) sample; implement repeated multimodal assessments; map trajectories and outcomes over a 2 year period (conversion to psychotic disorder, persistent and incident non-psychotic disorders, non-remission of CHR status, persistent negative symptoms, psychosocial functioning, full recovery). This network of CHR recruitment centres will provide the clinical research infrastructure for future treatment trials in this clinical population informed by findings from the current program of work.

2. Prediction: In collaboration with the NIMH Steering Committee and the DPACC, the PRESCIENT dataset will be used to:

2a. Test the external validity of existing and forthcoming prediction models in the field (e.g., NAPLS, EU-GEI, PRONIA, PSYSCAN).

2b. Implement the model with strongest performance as an online risk calculator.

2c. Use the full AMP SCZ dataset to develop new, more refined prediction models and risk calculators drawing on recent theoretical and methodological advances (e.g., dynamic prediction, probabilistic multimodal modelling) and a range of biomarkers. These tools will guide stratification of patients in future clinical trials and may have clinical utility in decision making about stepping interventions up/down as risk is assessed over time (clinical trajectory, treatment response) and in response to incoming biomarker information, as well as guide stratification of patients in future clinical trials.

3. Validation: Internally and externally validate the prediction models generated in the AMP SCZ dataset. This will test the robustness, replicability and generalisability of the models' performance.

The purpose of recruiting a sample of healthy control participants is primarily to model site effects of biomarker measurement, particularly for neuroimaging data. However, this cohort also serves the purpose of: providing benchmark ‘normal’ levels on the various measures included in the schedule of assessments; modelling age effects; and assessing the stability of the biomarkers in healthy individuals.

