7.2. Sample Size and Power

The size of the CHR sample is primarily determined by the aim of developing a prediction model for conversion to psychosis by 24 months (the primary outcome of interest). This will be achieved by combining data from the PRESCIENT and ProNET networks (i.e., the AMP SCZ dataset as whole), given that the protocols and schedule of assessments have been harmonised across the two networks. The projected CHR sample size for PRESCIENT is 937 and for ProNET 1,040 (combined n of 1,977). There is no uniform method for determining an adequate sample size for developing a prediction model⁹². In this sample size calculation, the method recently described by Riley et al⁹³ was used. Minimum sample size calculations required for various scenarios are provided in table 1. below. Specifically, the sample sizes were derived for the scenarios of having low, medium or high prediction performance and also for the number of parameters in the model being 10, 20, 30, 40 or 50. Conversion to psychosis is a time-to-event outcome and therefore a survival model such as Cox regression is appropriate. The table below shows the sample sizes for the survival outcome, assuming a conversion rate of 15% over 2 years (number of events=300).

Table 1. Minimum sample sizes for survival outcome.

		Number of parameters in model				
		10	20	30	40	50
Predictive performance	low	422	843	1265	1686	2108
	medium	398	796	1193	1591	1989
	high	366	732	1098	1464	1830

It is undesirable to have the number of parameters above 30 as this would result in a prediction model that is overly cumbersome in real-world settings. As indicated in the table, the minimum sample size for a model with 30 parameters is estimated to be between 1100 and 1300. However, as in all medical research, larger sample sizes lead to more robust models and it would therefore be desirable to achieve a sample size larger than this minimum recommendation. Therefore, we aim to assemble as large a sample as possible given the constraints of the length of the recruitment period and the number of recruitment sites. The sample size calculations presented in the table indicate that the overall AMP SCZ sample size of 1,977 is adequate for developing a prediction model with ~30 parameters that has high predictive performance, while still allowing a subset of the data to be 'held back' for external validation purposes (see section 14).

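### The existing model that ranks best in PRESCIENT is treated as externally validated by that same ranking, and no independent check of it is planned before it becomes a risk calculator

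*Protocol*

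**What the plan says.** The objectives (Synopsis and Section 5.4) assign the PRESCIENT dataset to aim 2a, testing existing and forthcoming models, and to aim 2b, putting the strongest one into use. Only aim 2c moves to the combined AMP SCZ data. Aim 2b in the Synopsis reads: "Implement the model with strongest performance as an online risk calculator that can be calibrated for service setting". Section 5.4 gives the same rule without the calibration clause.

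Section 14, under aims 2a and 2b, says of the existing models that "the one that shows the strongest performance in the PRESCIENT sample may be made into an online risk calculator". The use it has in mind is described as preliminary and confined to certain clinical services. Because PRESCIENT recruits from primary and specialist services, it adds that "the risk calculator will be able to be calibrated for type of recruitment/service setting". It then describes the whole exercise as validation: "This use of the PRESCIENT dataset to externally validate existing and forthcoming prediction models will address one of the key limitations in the field".

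Independent testing appears only under aim 3: "Internally and externally validate the prediction models generated using the AMP SCZ dataset". The last part of Section 14 implements this by holding back a subset of sites from the development of new models, with calibration intercept, slope and discrimination to be assessed there. No corresponding step is described for the chosen existing model.

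**The concern.** Each candidate was built elsewhere, so its performance in PRESCIENT is a fair external estimate for that model taken alone. That changes once several models are ranked on one sample and the top one is kept. The highest of several noisy estimates is on average too high, and the model that produced it need not be the best.

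The same applies to calibration. An intercept and slope fitted by service setting in PRESCIENT will fit PRESCIENT by construction, which says nothing about how well the risks hold for new patients.

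The protocol gives new models a held-back sample. The existing model, which Section 14 names for preliminary clinical use, gets only the sample that chose it. Users told that it was externally validated in PRESCIENT could take a selected figure for an independent one.

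**Working it through.** **Inputs from the Protocol.** Section 7.2 gives 937 CHR participants for PRESCIENT, 1,040 for ProNET and 1,977 combined, with 15% converting over 2 years and 300 events. The number of candidate models is not fixed: Section 14 refers to published models covered in several reviews and names four forthcoming sources.

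**Assumptions.** 3 to 20 models compared; correlation between their estimates 0 to 0.8; true concordance around 0.70.

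**Step 1, the plan's own figure.** 1,977 × 0.15 = 296.6, which agrees with the stated 300. The protocol gives no performance figure for the chosen existing model, so there is none to reproduce.

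**Step 2, events by network.** PRESCIENT: 937 × 0.15 = 140.6, about 141 events and 796 non-events. ProNET: 1,040 × 0.15 = 156.

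**Step 3, precision of one estimate.** Hanley-McNeil, with A = 0.70, n1 = 141, n0 = 796:

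SE² = [A(1−A) + (n1−1)(Q1−A²) + (n0−1)(Q2−A²)] / (n1·n0), where Q1 = A/(2−A) = 0.5385 and Q2 = 2A²/(1+A) = 0.5765.

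SE² = [0.21 + 140 × 0.0485 + 795 × 0.0865] / 112,236 = 0.000675, so SE = 0.026. It is 0.031 at a 10% conversion rate and 0.023 at 20%.

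**Step 4, expected optimism of the winner.** For K equally good models with correlation ρ, optimism = E[max of K standard normals] × SE × √(1−ρ). Example: K = 10, ρ = 0.5 gives 1.54 × 0.026 × 0.707 = 0.028. The two right-hand columns are simulated and let true concordance vary between models with SD 0.02.

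| Models | Equal, ρ = 0.8 | Equal, ρ = 0.5 | Equal, ρ = 0 | Differing, ρ = 0.8 | Differing, ρ = 0 |
|---|---|---|---|---|---|
| 3 | 0.010 | 0.016 | 0.022 | 0.005 | 0.017 |
| 5 | 0.014 | 0.021 | 0.030 | 0.007 | 0.024 |
| 10 | 0.018 | 0.028 | 0.040 | 0.009 | 0.032 |
| 20 | 0.022 | 0.034 | 0.049 | 0.011 | 0.038 |

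When true performance differs in this way, the selected model is not the truly best one in 24% (K = 3, ρ = 0.8) to 72% (K = 20, ρ = 0) of runs.

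**Step 5, patient-level check.** With 141 events, 796 non-events and all true values at 0.70, the winner's mean concordance in the selecting sample is 0.712 to 0.727 for 5 models and 0.717 to 0.736 for 10 (ρ from 0.8 to 0). The same winner in a fresh sample of 937 returns 0.699 to 0.701. The excess therefore comes from selection.

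**Step 6, recalibration.** An intercept and slope were fitted in each of two simulated settings (937 patients, logistic model). The calibration slope in the fitting data is exactly 1.00. In a new sample of 1,040 its mean is 0.98, with a 5th to 95th percentile range of 0.70 to 1.29. That range includes the sampling error of the slope in the new sample as well as error in the fit. The average loss is small, but the apparent slope carries no information.

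**The case against.** Three arguments on the other side have weight.

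First, Section 14 calls itself a broad outline, and a statistical analysis plan that is not shown could add an optimism correction or a ProNET check. That is fair for the details. The allocation of data to aims, however, is fixed in the objectives: PRESCIENT for choosing, the hold-out for new models only, and the label of external validation for the ranking step. The gap lies in that allocation.

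Second, a reader might infer that the protocol commits to recalibrating the winner and publishing its uncorrected PRESCIENT performance. The text does not support this. Calibration by setting is worded as a capability, release is conditional in Section 14 (though not in aim 2b), and no rule says which performance figure accompanies the calculator. Inflation follows only if the PRESCIENT figure is the one quoted.

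Third, a reader might infer that a model truly below a concordance of 0.7 could pass the protocol's threshold through selection. The value 0.7 stands in the paragraph on developing new models, as a description of good performance. It is not a release criterion for existing models, so there is no gate to pass wrongly. The clinical use described is also limited, with referral for further assessment as the example.

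The discrimination bias is modest, too. For 5 equally good models it is mostly below one standard error, and it shrinks when models are highly correlated or clearly differ. Finally, ProNET is not shown to have the primary and specialist split on which setting-specific calibration rests, so it may not be able to check that part.

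**Conclusion.** The point holds as a gap in the design. The protocol ranks existing models in PRESCIENT, names PRESCIENT as the basis for calibrating the winner by setting, calls the same use external validation, and extends no independent check to the model chosen. It does not establish that any published figure will be inflated.

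If the winner's PRESCIENT concordance is quoted, the expected optimism is about 0.014 to 0.030 for 5 and 0.018 to 0.040 for 10 equally good models, and about 0.005 at the low end (3 models, correlation 0.8, differing true performance). This rests on the assumed number of models, correlation and true concordance, and on the protocol's 15% conversion rate. Apparent calibration after any setting-specific refit would be perfect by construction. The matter should be corrected, but it does not undermine the study's main aims.

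**What to change.** Keep the ranking, and any recalibration, in PRESCIENT. Add to Section 14, and reflect in aim 2b, a statement that the discrimination and calibration figures accompanying any released calculator come from data not used to choose or calibrate it. ProNET is the natural source: 1,040 projected CHR participants, about 156 conversions at 15%, a standard error of about 0.025 at a concordance of 0.70, and a harmonised battery (Section 5.1.3). Its use under aim 2c is no obstacle, because this check fits nothing to the ProNET data.

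Where ProNET lacks the primary and specialist split, check the setting-specific calibration in PRESCIENT sites of both types that were left out of the ranking and calibration. Alternatively, use a bootstrap optimism correction that repeats both the selection and the recalibration in every resample. Describe the PRESCIENT results as a comparison of models, and keep the term external validation of the calculator for the independent figures.

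The cost is one extra analysis on data already being pooled, a slightly less favourable headline figure, and a wait for ProNET outcomes. Holding back PRESCIENT sites, if that route is taken, also leaves fewer events for the ranking.
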